5.2 EXCLUSION CRITERIA

In order to be eligible to participate in this study, an individual must not meet any of the following criteria:

1. Current or prior treatment with rituximab, belimumab or any other biologic agent in the 6 months prior to screening.
2. Current treatment with methotrexate, azathioprine, mycophenolate mofetil, cyclosporine, tacrolimus, or other less common immunomodulatory drugs such as those falling into the class of disease-modifying antirheumatic drugs (DMARDs), not otherwise specified herein. Participants previously on methotrexate, azathioprine, mycophenolate mofetil, cyclosporine or tacrolimus, or other DMARDs should have withdrawn drug for at least 8 weeks (56 days) at the time of screening.
3. Treatment with cyclophosphamide, pulse methylprednisolone or IVIG within 6 months prior to screening.
4. Current treatment with potent inhibitors of Cytochrome P450 3A4 (CYP3A4) (e.g., ketoconazole) or receiving one or more concomitant medications that result in both moderate inhibition of CYP3A4 and potent inhibition of CYP2C19 (e.g., fluconazole) that would increase serum availability of Tofacitinib. Past treatment with the aforementioned agent is allowed if it was more than a week prior to the administration of the first dose of study medication.
5. History of chronic liver disease, not including well-controlled Sjogren's-related chronic liver disease or elevated LFTs:
 - ALT or AST \geq 2x upper limit of normal at screening
 - Serum unconjugated bilirubin $>$ 2mg/dL at screening
6. Serum creatinine $>$ 1.5mg/dL.
7. Protein to creatinine ratio of more than 1mg/dL at screening (repeated and confirmed three times or confirmed with 24 hours urine protein of more than 1000 mg).
8. Active urinary sediment (WBC, RBC or mixed cellular casts 1+ or more /hpf).
9. Hypercholesterolemia: Values after 8-12 hour fasting blood specimen: total cholesterol $>$ 250 mg/dL or LDL $>$ 180 mg/dL or hypertriglyceridemia (triglyceride $>$ 300 mg/dL) within - 45 days of screening visit.
10. WBC $<$ 2500/ μ L or ANC $<$ 1,000/ μ L, Hgb $<$ 9.0 g/dL or platelets $<$ 70,000/ μ L or absolute lymphocyte count $<$ 500/ μ L.
11. Pregnant or lactating women. Women of childbearing potential are required to have a negative pregnancy test at screening.
12. A history of drug or alcohol abuse within the 6 months prior to screening.
13. Currently receiving hemodialysis, peritoneal dialysis, or intestinal dialysis.

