14. Active infection that requires the use of oral or intravenous antibiotics unresolved at least 14 days prior to the administration of the first dose of study medication.
15. Active chronic infections including but not limited to HIV, Hepatitis B, Hepatitis C, and BK viremia at screening visit.

16. Current or previous diagnosis of malignant disease, except for basal cell or squamous cell carcinoma of the skin with complete excision and clear borders or adequately treated in situ carcinoma of the cervix.
17. Known active tuberculosis. Participants with treated latent tuberculosis (LTB) will be eligible to participate. Participants with untreated LTB will not be excluded but will be evaluated by an infectious disease (I.D.) consultant and may become eligible for trial based on infectious disease consultant recommendations.
18. History of severe or systemic infection caused by common pathogens, or history of infection with pathogens that normally do not cause human disease.
19. Participants with active renal or central nervous system disease or a high activity level in any organ system (except articular) in ESSDAI⁵⁴.
20. Participants with known increased risk factors for major adverse cardiac event (MACE) including a history of:
 - Ischemic heart disease (e.g., history of acute myocardial infarction)
 - Heart failure
 - Cardiomyopathy
 - Severe valvular heart disease
 - Significant arrhythmias
 - Chronic renal failure
 - Cerebrovascular accident or transient ischemic attack
 - Uncontrolled diabetes mellitus
 - Uncontrolled hypertension
 - Current smokers or former smokers with less than 3 years since complete cessation and/or >20 pack-years of smoking history.
21. Significant impairment of major organ function (lung, heart, liver, kidney) or any condition that, in the opinion of the Investigator, would jeopardize the participant's safety following exposure to the study drug.
22. Known history of arterial or venous thrombosis or at high risk for clotting disorder
23. Psychiatric illness or history of medical non-compliance that the study team feels will make the patient unlikely to complete the study
24. Uncontrolled thyroid disease as per PI or medically responsible investigator.
25. Known allergic reactions to Tofacitinib or its components
26. Treatment with another investigational drug/intervention within six months except for COVID-19 vaccines or therapies that have been granted an FDA emergency authorization.

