 - A 35-day supply of study drug or placebo will be dispensed to participants on study day 1 with instructions regarding twice daily dosing regimen and a review of potential side effects. No drug will be dispensed to a female participant of reproductive potential until negative pregnancy test results (serum or urine) have been obtained within 24 hours.

Abbreviated Title: Tofacitinib in Sjögren's syndrome

Version Date: 07/01/2024

- For acute infection(s) requiring antibiotics discovered on Day 1: Any participant found to have an acute infection at baseline visit (Day 1 visit) will have the study drug withheld and their next visit will be scheduled for no more than 30 days later;
- Infections prior to 14 days of Day 1: study medication may be administered
- Between -14 to Day 1: study drug will be delayed up to the upper limit of 45 days from screen date
- If the above stated 14 days puts the patient beyond the limits of protocol mandated pre-screening interval, the participant will be excluded from study participation and then give the opportunity to be re-evaluated and re-enrolled.
- If the infection resolves, study medication will be started. If infection does not resolve within 30 days the participant will be removed from the study
- If a medically significant abnormal lab result (i.e., complete blood count, serum chemistries, pregnancy test, urinalysis and random urine protein/creatinine ratio) occurs at baseline (Day 1 visit), requiring repeat for confirmation, the study drug will be withheld and the next visit will be scheduled no more than 30 days later; if repeat testing reveals resolution of abnormal results, participants will be instructed to begin study medication. If the abnormal lab result does not resolve, participants will be removed from the study. Vascular function studies or research labs will not be repeated.

Study Days 7, 21, 42, 70, 154 (+/- 3 days) Telephone Calls

All participants will receive a telephone call from the study coordinator on study days 7, 21, 42, 70, and 154 (+/- 3 days). These calls will confirm study drug compliance, document any adverse events, and record any new or discontinued concomitant medications. A script with standardized questions will be used to confirm compliance with study drug.

Study Day 14/Visit 3: (on site visit)

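### The closing Day 1 infection bullet starts study drug on resolution without the 14-day or 45-day limits, so read literally it can dose a participant whom exclusion 14 bars

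*Combined protocol and SAP*

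**What the plan says.** Section 5.2 opens with "In order to be eligible to participate in this study, an individual must not meet any of the following criteria". Criterion 14 is an active infection needing oral or intravenous antibiotics that is "unresolved at least 14 days prior to the administration of the first dose of study medication". The interval is counted back from the first dose, not from screening.

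Section 8.2.1, Study Day 1/Visit 2, then gives a list for acute infections that need antibiotics:

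- If one is found on Day 1, drug is withheld and "their next visit will be scheduled for no more than 30 days later".
- An infection more than 14 days before Day 1 does not prevent dosing.
- For a more recent infection the rule reads "Between -14 to Day 1: study drug will be delayed up to the upper limit of 45 days from screen date".
- Where a 14-day wait overruns the screening interval, the outcome is that "the participant will be excluded from study participation and then give the opportunity to be re-evaluated and re-enrolled".
- The closing bullet: "If the infection resolves, study medication will be started". It continues: "If infection does not resolve within 30 days the participant will be removed from the study".

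Section 7.2 also lists a treatment delay of more than 45 days after screening, but only among reasons for which an investigator may withdraw someone. The Schedule of Activities (Section 1.3) marks the review of inclusion and exclusion criteria at the screening visit only.

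**The concern.** The closing bullet is the instruction staff will have in front of them when a held participant returns. It names one condition (resolution) and one time limit (30 days). It does not mention the 14 infection-free days or the 45 days from screening. An investigator who follows it as written can start drug within days of an antibiotic-requiring infection. An investigator who follows the bullet above, or exclusion 14, would wait or exclude the same participant.

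What is at stake is participant safety and consistent eligibility. The drug is an immunosuppressant whose boxed warning (Section 2.4.1) begins with serious infections, and safety is the trial's primary objective.

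**Working it through.** The plan gives no figure to reproduce. The check is date arithmetic.

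**Inputs**

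- d = days from screening to Day 1, from 0 to 45 (screening window, Sections 1.3 and 8.1.1).
- r = days from Day 1 to resolution. The closing bullet accepts r ≤ 30.
- Infection-free interval before the first dose: 14 days (exclusion 14).
- Limit from screening: 45 days (Day 1 infection list, Section 8.2.1).

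**Step 1: exclusion 14 alone.** The closing bullet permits a dose at any time once the infection has resolved. Exclusion 14 requires the dose at r + 14 or later. Suppose resolution comes on day 25 and drug is started at a visit 30 days after Day 1. The infection-free interval is 30 − 25 = 5 days. With resolution on day 30 it is 0 days. Waiting longer would satisfy exclusion 14, but the bullet does not ask for a wait.

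**Step 2: both limits together**, taking the 45-day bullet to include infections found on Day 1.

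d + r + 14 ≤ 45, so d + r ≤ 31 and the latest permitted r is 31 − d.

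| d | Latest r meeting both limits | r accepted by the closing bullet but excluded by the others |
|---|---|---|
| 1 | 30 | none |
| 7 | 24 | 25 to 30 |
| 14 | 17 | 18 to 30 |
| 21 | 10 | 11 to 30 |
| 28 | 3 | 4 to 30 |
| 31 or more | none (r of at least 1) | 1 to 30 |

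**Step 3: two worked cases at d = 20.**

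- r = 10: the earliest permitted dose is 20 + 10 + 14 = day 44, inside 45. Waiting meets every rule.
- r = 15: the earliest permitted dose is 20 + 15 + 14 = day 49, beyond 45. The bullet above excludes. Because 15 ≤ 30, the closing bullet starts drug.

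**Step 4: if drug is started at the rescheduled visit**, v days after Day 1 (v ≤ 30), both limits need r ≤ v − 14 and d ≤ 45 − v.

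- v = 30: r ≤ 30 − 14 = 16 and d ≤ 45 − 30 = 15.
- v = 21: r ≤ 21 − 14 = 7 and d ≤ 45 − 21 = 24.

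On that assumption, resolution on days 17 to 30 can never leave 14 clear days by the visit. The plan does not say that drug must start at that visit, so this step is conditional.

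**The case against.** The strongest reply is that both limits already stand in the same list, directly above the sentence. Read in order, the closing bullet covers only those not already excluded. It gives no start date, so it does not order dosing on the day of resolution, and exclusion 14 applies regardless. Dispensing also needs investigator approval (Section 6.2.1), exclusion 21 bars anyone whose safety the investigator thinks would be at risk, and Section 6.1.2 allows dispensing at unscheduled visits, so a 14-day wait is workable.

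Much of this stands. A reader might infer that the plan has no infection-free interval or no limit on the delay. It has both. A reader might also infer that the rules always collide. They do not: exclusion 14 alone can be met by waiting, and the outright contradiction depends on applying the 45-day bullet to an infection found on Day 1. Its range runs up to and names Day 1, so that is the natural reading, but it is still an inference. Section 7.2 supports it only through a discretionary withdrawal reason.

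What does not stand is that the text settles the matter. The closing bullet is not worded as subject to those above it, and it attaches a 30-day limit of its own. Investigator approval does not say which instruction governs, and no eligibility recheck is scheduled after screening.

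A reader might extend the point to the hold for abnormal Day 1 laboratory results. The documents do not support that: the hold contradicts no exclusion criterion, and a mandatory 45-day cap there would turn a discretionary reason into a new rule.

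**Conclusion.** The point holds as a conflict of wording with a safety consequence. Followed literally, the closing bullet permits a first dose less than 14 days after an antibiotic-requiring infection resolves, contrary to exclusion 14. If the 45-day bullet covers infections found on Day 1, then for d + r > 31 with r ≤ 30 one bullet says start and the one above says exclude, and no waiting period reconciles them.

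The size is small. The documents give no rate for Day 1 holds, and few participants are likely to be affected. A reader might infer a threat to the treatment comparison. The documents do not support that: the trial is double-blind and the same rule applies to both arms. A held participant who is never dosed enters neither the safety population nor the intent-to-treat population (Sections 9.2.1 and 9.2.2). No sample size, endpoint or analysis changes.

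**What to change.** Replace the closing sentence with:

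> Study drug will be started only when at least 14 days have passed since the infection resolved and no more than 45 days since the screening visit; otherwise the participant will be excluded and may be re-evaluated and re-enrolled.

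Keep the visit within 30 days as the check on resolution, and keep removal if the infection has not resolved by then. Both limits and the re-enrolment route are already in the plan. The new sentence also makes explicit that the 45-day limit covers infections found on Day 1.

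The cost is one sentence in an amendment. A few held participants will be re-screened or replaced instead of dosed late. Some may already be randomised but not dosed, because randomisation follows confirmation of eligibility and is scheduled for Day 1. Section 7.2 provides for replacing such participants, and each replacement draws on the up to 11 additional places in Section 4.1.

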8.2.3 Duration of Study Participation

Study participation will be a maximum of 241 days, comprised of a 45 day screening period 168 days treatment period, and 28 day follow up period. All study time periods are inclusive of a window of +/- 7 days for study days 1, 28, 56, 84, 112, 140, -7 days for study day 168 and +/- 3 days for telephone calls to accommodate any potential variability in participant scheduling (see Schedule of Events).

8.2.4 Vital Signs Measurement

Vital signs measurements will include pulse rate, systolic and diastolic blood pressure, respiratory rate, and temperature. These measurements will be performed at all study visits and recorded on CRF.

8.2.5 Adverse event assessment

Adverse events will be assessed by reviewing the interim medical history, performing a physical evaluation, asking open-end question of how the participant's feeling and reviewing laboratory results at each visit, as well as part of the clinical monitoring telephone calls on study days 7, 21, 42, 70, and 154 (+/- 3 days) as per Section 5.1.2.. After completing screening assessments, any adverse event (AE) or serious adverse event (SAE) reported by a subject, whether or not study drug has been administered, will be recorded by the investigators. Any AE/SAE prior to dosing will be categorized as "Baseline" and any AE/SAE after dosing will be categorized as "treatment-emergent."

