2.4.2 Risks associated with study procedures

Minor Salivary Gland Biopsy

The biopsy will be performed according to NIDCR SOPs. Local anesthetic will be administered to minimize pain during the procedure. Biopsy of the MSG may cause discomfort, pain, and swelling at the site (usually lower lip) for several days following the procedure; these symptoms can be effectively treated with ibuprofen, acetaminophen, or more potent analgesics as needed. Participants may also experience transient paresthesia in the region of the biopsy, permanent paresthesia, although reported, are exceedingly rare using the techniques employed by the NIDCR. Other possible risks are allergic reactions to the local anesthetic and bleeding and infection at the site of biopsy however, such events are rare.

In a retrospective analysis of biopsies performed in our Clinic, aphthous ulcers developed in less than 5% of volunteers who participated in our study. Although the exact cause was not identified, this is well-known risk associated with the mucosal biopsy and anesthetic injection. Post-operative checks are routinely accomplished 4 to 7 days after the procedure for suture removal. Typically, resorbable sutures are used and no follow up is necessary. Rarely a

Abbreviated Title: Tofacitinib in Sjögren's syndrome

Version Date: 07/01/2024

participant will have defective healing, forming an epithelial tag or mucocele. These are surgically correctable and will be addressed by an NIDCR dentist or oral surgeon.

Salivary Gland Ultrasound

There are no known risks of salivary gland ultrasounds. This procedure is generally considered safe. Patients may experience slight discomfort (cold feeling of the skin) on the areas of the face where transduction gel is applied.

Collection of Saliva/Measurement of Salivary Flow Rate

There is no known risk associated with this salivary collection. Participants may experience mild discomfort due to increased dryness caused by withholding salivary stimulants for 24 hours prior to saliva collection. There may be mild discomfort due to positioning of mouth during saliva collection. Citric acid (lemon juice) solution used to stimulate salivary flow may cause an unpleasant taste and mild discomfort in the salivary glands if the parotid duct is blocked and saliva cannot be expressed.

Vascular function studies: SphygmoCor, CAVI and Endopat

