While on this study, participants will continue to receive regular medical care from their primary physicians. Any AEs reported will be followed by the investigators as described in Section 16.1.8. Following completion of the study or after withdrawal from the study, participants will return to the care of their referring physicians. Participants may continue their follow up visits on protocol 15-D-0051 as appropriate. A summary of the participants' course in the study will be sent to the referring physician.

Participants who withdraw or are withdrawn from the study after receiving study treatment will be asked to complete the day 168 and 196 for close out safety assessments. Participants are deemed ineligible before study day 1 or randomization will resume care with their referring physician with no further evaluation in this protocol.

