8.6 ADVERSE EVENTS AND SERIOUS ADVERSE EVENTS

8.6.1 Definition of Adverse Event

Adverse events (AE) are any unfavorable and/or unintended diagnosis, symptom, sign (including an abnormal laboratory finding), syndrome, or disease that occurs during the study, having been either absent at baseline, or if present at baseline, appears to worsen.

Events will be reported as AE's as described in section 8.2.5.

All AEs will be graded for intensity (severity) according to CTCAE version 5.0 and relationship to study drug as described below.

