8.7.4 Time Period and Frequency for Event Assessment and Follow-Up

The occurrence of an adverse event (AE) or serious adverse event (SAE) may come to the attention of study personnel during study visits and interviews of a study participant presenting for medical care, or upon review by a study monitor.

All AEs including local and systemic reactions not meeting the criteria for SAEs will be captured on the appropriate case report form (CRF). Information to be collected includes event description, time of onset, clinician’s assessment of severity, relationship to study product (assessed only by those with the training and authority to make a diagnosis), and time of resolution/stabilization of the event. All AEs occurring while on study must be documented appropriately regardless of relationship. All AEs will be followed to adequate resolution.

Any medical condition that is present at the time that the participant is screened will be considered as baseline and not reported as an AE. However, if the study participant’s condition deteriorates at any time during the study, it will be recorded as an AE.

The severity of an AE will be documented at its highest level of severity. AEs characterized as intermittent require documentation of onset and duration of each episode.

Any time after informed consent is obtained, AEs and SAEs will be recorded and reported until 7 (for non-serious AEs) or 30 days (for SAEs) after the last day of study participation.

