9.3.2 Analysis of the Primary Endpoints

The primary goal is to evaluate the safety and tolerance of Tofacitinib in participants with SS. For the safety population, the number and percentage of subjects with any AE, any related AE, any SAE, any Grade 3 and 4 toxicities not fulfilling the criteria for SAE, and non-serious adverse events and SS disease flares, as well as the total number of events for each category will be summarized by treatment group. AE's/SAE's will be reported from the time of consent. Events that are reported prior to the first treatment will be considered non-treatment emergent in analyses.

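### The protocol gives two start points for adverse-event recording (end of screening in 8.2.5 and the schedule, consent in 8.7.4 and 9.3.2), and 9.3.2 sorts treatment-emergence by report rather than onset

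*Combined protocol and SAP*

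**What the plan says.** Four parts of the protocol bear on when recording starts.

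- **8.2.5** describes the events to be recorded as "After completing screening assessments, any adverse event (AE) or serious adverse event (SAE) reported by a subject", whether or not drug has been given. It then adds a label: "Any AE/SAE prior to dosing will be categorized as" Baseline, with later events called treatment-emergent.
- **8.6.1** sends the reader back to that rule: events are reported "as described in section 8.2.5".
- **8.7.4**, the section on the time period for event assessment, says: "Any time after informed consent is obtained, AEs and SAEs will be recorded and reported". It lists time of onset among the items collected and says that all events are followed to adequate resolution.
- **9.3.2**, the primary safety analysis, says events are "reported from the time of consent. Events that are reported prior to the first treatment will be considered non-treatment emergent".

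The schedule in 1.3 (as extracted) has no adverse-event review at screening; the first mark is at Day 1. The screening procedure list in 8.1.1 has no such review either, while the Day 1 list in 8.2.1 does.

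For people found ineligible before Day 1 or randomisation, 8.2.2 says they "will resume care with their referring physician with no further evaluation in this protocol". Section 5.4 sets a minimum data set for screen failures that names serious adverse events but not non-serious ones.

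**The concern.** Safety is the primary endpoint, and screening is not event-free. It includes a minor salivary gland biopsy, for which 2.4.2 lists pain, swelling, paresthesia, bleeding, infection and ulcers. Staff working from 8.2.5 and the schedule would not ask about these during screening; staff working from 8.7.4 would. The analysis in 9.3.2 assumes the second practice. Two coordinators could both follow the protocol and produce different pre-dose records.

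The classification rule is a separate weakness. 9.3.2 sorts by when an event was reported, and 8.2.5 does not say whether its pre-dose and post-dose labels refer to onset or to report. The tables in 9.3.2 count any adverse event and total events by arm, not only drug-related Grade 3 or higher toxicity, so a mislabelled minor event would show.

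**Working it through.** **Start point, followed through by when an event is reported**

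| Event first reported | 8.2.5 and schedule | 8.7.4 and 9.3.2 |
|---|---|---|
| Before screening is complete | Not in scope | Recorded, non-treatment-emergent |
| After screening, before first dose | Recorded as Baseline | Recorded, non-treatment-emergent |
| After first dose, onset before it | Recorded; label unclear | Recorded; treatment-emergent on a literal reading |

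The first row is the contradiction. The third row is the classification problem. It would remain even if 8.2.5 already began at consent, because it comes from the word reported in 9.3.2.

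**Who is exposed to the first row.** A randomised participant has an adverse-event review and an oral examination at Day 1, so a complication can still be picked up then. A screen failure has neither. Section 4.1 gives up to 76 screened and 30 randomised plus up to 11 more, that is 30 to 41. If all 76 places are used, 76 − 41 = 35 to 76 − 30 = 46 people are never randomised.

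**Scale of biopsy events.** The only rate in the protocol is in 2.4.2: "aphthous ulcers developed in less than 5% of volunteers who participated in our study". Expected count = n × p, with p = 0.05 as an upper bound and every participant assumed to have a screening biopsy:

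- 30 randomised: 30 × 0.05 = 1.5; chance of at least one = 1 − 0.95^30 = 0.785.
- 41 randomised: 41 × 0.05 = 2.05; chance of at least one = 1 − 0.95^41 = 0.878.
- At an assumed 1%: 30 × 0.01 = 0.3 and 41 × 0.01 = 0.41.

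These are ceilings. Under 8.1.1 a companion-protocol biopsy from the last twelve months may serve as baseline. The documents do not give the fraction of ulcers that would go unreported until after dosing.

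**Effect of one misclassified participant.** With the planned 20 and 10, and if that participant has no other event in the category, the proportion moves by 1/20 = 5 points on Tofacitinib or 1/10 = 10 points on placebo. Replacements under 7.2 enlarge the denominators: 41 split 2:1 is about 27 and 14, giving 1/27 = 3.7 and 1/14 = 7.1 points.

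**The case against.** The strongest reply is that the damage is small and the protocol has safeguards.

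- Section 8.2.5 has its own Baseline category, so a complication reported between screening and dosing is recorded and kept out of the treatment-emergent counts.
- A lip ulcer or infection would have to escape the Day 1 review, physical examination and oral examination before first being mentioned at the Day 7 call.
- Onset time is collected, and 8.6.1 counts only events absent at baseline or worsening, so an analyst could still class such an event correctly.
- Under 8.7.2, causality to study procedures is judged separately from causality to drug. A recognised biopsy event therefore need not enter the toxicity definition of a drug-related Grade 3 or higher event.
- Pre-dose events should not differ systematically by arm, and 9.1 calls all analyses descriptive.

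All of this stands, and it limits the point. It does not remove the conflict over the start date, and it does not help screen failures, who never reach Day 1.

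A reader might go further and infer that screening-biopsy complications are bound either to be lost or to surface as treatment-emergent, that the consent-to-dose listing cannot be produced, or that harms in screen failures are neither recorded nor followed. The documents do not support this. The Baseline route is a third outcome. Section 8.7.4 requires recording from consent. Section 8.2.2 also says that reported events will be followed by the investigators. Section 5.4 sets a floor, not a limit. Nor should an ulcer count based on all 76 screened be set against the treatment-emergent tables, because only randomised participants can enter them.

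**Conclusion.** The protocol contradicts itself on when adverse-event recording starts. The supportable consequence is inconsistent capture of non-serious screening events, most likely in screen failures. The reported-based rule in 9.3.2 is a second, independent defect that permits, but does not force, misclassification of pre-dose events.

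The likely size is small: at most about 1.5 to 2 expected ulcers among those randomised, of which an unknown part could be mislabelled, with noise rather than directional bias between arms. These figures assume the 5% upper bound and a screening biopsy for everyone. They cover ulcers only, since the protocol gives no rate for the other biopsy complications. The point still merits correction because it concerns the primary safety data, and with 20 against 10 participants a single mislabelled person is visible.

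**What to change.** 1. In 8.2.5, start recording at signed informed consent, in line with 8.7.4 and 9.3.2; 8.6.1 then points to the right rule without change.
2. Mark adverse-event review at the screening visit in the schedule, and add it to the screening list in 8.1.1.
3. Reconcile the sentence in 8.2.2 that ends evaluation of ineligible participants with the 8.7.4 statement that all events are followed to resolution, for example by excepting ongoing adverse events.
4. In 9.3.2 and 8.2.5, define treatment-emergence by onset relative to first dose, using the onset time already collected.

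The cost is a few words in each place, one schedule cell, and slightly more adverse-event recording at screening visits that already take place. No new data item is needed.
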